16.2 ECOG Performance Status Criteria

Grade	Description	
0	Normal activity. Fully active, able to carry on all pre-disease performance without restriction	
1	Symptoms but ambulatory. Restricted in physically strenuous activity, but ambulatory and able to carry out work of a light or sedentary nature (e.g., light housework, office work)	
2	In bed < 50% of the time. Ambulatory and capable of all self-care, but unable to carry out any work activities. Up and about more than 50% of waking hours.	
3	In bed $> 50\%$ of the time. Capable of only limited self-care, confined to bed or chair more than 50% of waking hours.	
4	100% bedridden. Completely disabled. Cannot carry on any self-care. Totally confined to bed or chair.	
5	Dead.	
Source: Oken MM, Creech RH, Tormey DC, Horton J, Davis TE, McFadden ET al. Toxicity and response criteria of the Eastern Cooperative Oncology Group. Am J Clin Oncol 1982; 5 (6):649-55.		

16.3 Contraception Requirements

Females of reproductive potential must agree to avoid becoming pregnant. Female of reproductive potential are required to use adequate methods of birth control from the time of screening (i.e., at least 14 days prior to D1 of SL-172154) through at least 30 days after the last dose of SL-172154.

Definition of Female of Childbearing Potential:

A female subject who is not sterile due to surgery (i.e., from bilateral tubal ligation/occlusion, bilateral ophorectomy, bilateral salpingectomy or complete hysterectomy) or who does not have a congenital or acquired condition that prevents childbearing or who is not naturally post-menopausal for at least 12 consecutive months.

Definition of Female of Non-Reproductive Potential:

Female subjects will be considered of non-reproductive potential if they:

1. Are post-menopausal if defined as amenorrhoeic for 12 consecutive months without an alternative medical cause. In women < 45 years of age a high follicle stimulating hormone (FSH) level in the postmenopausal range may be used to confirm a postmenopausal state in women not using hormonal contraception or hormonal replacement therapy. In the absence of 12 consecutive months of amenorrhea, a single FSH measurement is insufficient;

OR

2. Have had a hysterectomy and/or bilateral oophorectomy, bilateral salpingectomy or bilateral tubal ligation/occlusion, at least 6 weeks prior to screening;

OR

3. Have a congenital or acquired condition that prevents childbearing.

Definition of Male of Non-Reproductive Potential:

Male partners will be considered of non-reproductive potential if they have azoospermia (whether due to having had a vasectomy or due to an underlying medical condition).

Highly Effective Methods of Contraception (<1% failure rate):

For contraception, subjects should comply with one of the following:

1. Practice abstinence† from heterosexual activity;

OR

2. Use (or have their partner use) acceptable contraception during heterosexual activity.

Acceptable methods of contraception are *‡*:

- Single method (one of the following is acceptable):
 - intrauterine device
 - vasectomy of a female subject's male partner
 - contraceptive rod implanted into the skin
- Combination Methods
 - Female Subjects: The following hormonal contraceptives may be used by female subjects and requires use of a male condom for the male partner:
 - oral contraceptive pill (estrogen/progestin pill or progestin-only pill)
 - contraceptive skin patch
 - vaginal contraceptive ring
 - subcutaneous contraceptive injection

†Abstinence (relative to heterosexual activity) can be used as the sole method of contraception if it is consistently employed as the subject's preferred and usual lifestyle and if considered acceptable by local regulatory agencies and IRBs/Independent IECs. Periodic abstinence (e.g., calendar, ovulation, sympto-thermal, post-ovulation methods) and withdrawal are not acceptable methods of contraception.

‡If a contraceptive method listed above is restricted by local regulations/guidelines, then it does not qualify as an acceptable method of contraception for subjects participating at sites in this country/region.

Subjects should be informed that taking the study medication may involve unknown risks to the fetus (unborn baby) if pregnancy were to occur during the study. To participate in the study, subjects of childbearing potential must adhere to the contraception requirement (described above) from the time of screening and at least 14 days prior to D1 of SL-172154 through at least 30 days after the last dose of SL-172154.

16.3.1 Pregnancy Status

In the rare event that β -hCG is elevated as a tumor marker, pregnancy should be excluded. At minimum, this requires obstetrics evaluation, serial β -hCG measurements and ultrasound to exclude pregnancy.

16.4 Cockcroft-Gault Formula for Creatinine Clearance

Creatinine clearance $(mL/min)^1 = Q x (140 - age [yr]) x ideal body weight [kg]^2 72 x serum creatinine [mg/dL]$

Q = 0.85 for females Q = 1.0 for males

OR

Creatinine clearance $(mL/min)^2 = K \times (140 - age [yr]) \times ideal body weight [kg]^1$ serum creatinine [µmol/L]

K = 1.0 for females K = 1.23 for males

- 1. Creatinine clearance has a maximum value of 125 mL/min.
- 2. Use ideal body weight (IBW) if body weight > 30% of IBW. Otherwise, use bodyweight

Calculation of IBW using the Devine Formula [Devine, 1974]:

Males = 50.0 kg + (2.3 x each inch over 5 ft) or 50.0 kg + (0.906 kg x each cm over 152.4 cm)Females = 45.5 kg + (2.3 x each inch over 5 ft) or 45.5 kg + (0.906 kg x each cm over 152.4 cm)

Example:

Male, actual body weight = 90.0 kg; height = 68 inches; IBW = 50 + (2.3) (68 - 60) = 68.4 kg This subject's actual body weight is >30% over IBW. Therefore, in this case, the subject's IBW of 68.4 kg should be used in calculating the estimated creatinine clearance

References:

Devine BJ. Case Number 25 Gentamicin Therapy: Clinical Pharmacy Case Studies. Drug Intell. Clin Pharm. 1974;8:650-655.

Levey, A.S., J. Coresh, T. Greene, et al. (2006). Using standardized serum creatinine values in the modification of diet in renal disease study equation for estimating glomerular filtration rate. Ann Intern Med. 145:247-254.

Levey, A.S., L.A. Stevens, C.H. Schmid, et al. (2009). A new equation to estimate glomerular filtration rate. Ann Inter Med. 150:604-612.

16.5 **RECIST v1.1 and iRECIST Criteria**

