4.1 Participant Inclusion Criteria

Participants are eligible to be included in the study only if all the following criteria apply.

- 1. Subject has voluntarily agreed to participate by giving written informed consent in accordance with ICH/GCP guidelines and applicable local regulations.
- 2. Subject must have a histologically confirmed diagnosis of an unresectable, locally advanced or metastatic ovarian cancer, or primary peritoneal cancer or fallopian tube cancer.
- 3. Subjects must be refractory or intolerant to existing therapy(ies) known to provide clinical benefit for their condition. Subject must have received platinum-based therapies, and should not be eligible for further platinum therapy, or should be intolerant to such therapy. Subjects with known HRD positive disease may participate if they have received prior

polyadenosine diphosphate ribose polymerase (PARP) inhibitor therapy given alone or with bevacizumab. NOTE: HRD testing is not required per protocol.

- 4. Subjects should not be primary platinum refractory as defined by progressing during or within 1 month of upfront platinum therapy.
- 5. Has measurable disease by RECIST v1.1 using radiologic assessment.
- 6. Subject age is 18 years and older.
- 7. Has an Eastern Cooperative Oncology Group (ECOG) Performance Status of 0 or 1.
- 8. Has life expectancy of greater than 12 weeks.

9.	Laboratory val	lues must meet	the following	criteria.
----	----------------	----------------	---------------	-----------

Laboratory parameter	Threshold value
Absolute neutrophil count	$\geq 1.5 \ge 10^{9}/L$
(ANC)	without growth factor support
Platelet count	$\geq 75 \ge 10^{9}/L$
Hemoglobin (Hgb)	> 9.0 g/dL with no blood transfusions for at least 5 days prior to D1 of IP.
Creatinine clearance (CrCl)	≥ 30 milliliter (mL)/min (using modified Cockcroft-Gault formula; Appendix Section 16.4)
ALT/AST	\leq 3 x ULN
Total bilirubin	\leq 1.5 x ULN; subjects with isolated indirect hyperbilirubinemia are permitted if direct bilirubin ratio is <35% and total bilirubin is \leq 3.0 x ULN
Left ventricular ejection fraction (LVEF) by echocardiogram (ECHO)	\geq Lower limit of normal (LLN) per institutional threshold If LLN is not defined for a given institution, then ejection fraction must be \geq 50 %

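### The creatinine-clearance appendix behind the 30 mL/min entry criterion states a weight rule that its own worked example does not follow, and a female µmol/L constant that does not match its mg/dL formula

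*Protocol*

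**What the plan says.** Protocol Section 4.1, criterion 9 (repeated in the Synopsis) sets the renal threshold at "≥ 30 milliliter (mL)/min (using modified Cockcroft-Gault formula; Appendix Section 16.4". Sections 4 and 6 rule out waivers, so the appendix calculation alone decides a borderline case.

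Section 16.4 gives two formulas joined by OR:

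- The first takes creatinine in mg/dL, divides by 72, and uses "Q = 0.85 for females Q = 1.0 for males".
- The second takes creatinine in µmol/L and uses "K = 1.0 for females K = 1.23 for males".

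Both lines name ideal body weight as the weight term. Note 2 then gives the weight rule: "Use ideal body weight (IBW) if body weight > 30% of IBW. Otherwise, use bodyweight".

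The worked example is "Male, actual body weight = 90.0 kg; height = 68 inches; IBW = 50 + (2.3) (68 - 60) = 68.4 kg". It goes on: "This subject's actual body weight is >30% over IBW", and it uses IBW for that reason.

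The SAP contains no creatinine-clearance formula, and no other protocol section settles either point.

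**The concern.** Two parts of a half-page appendix disagree with themselves.

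**Weight rule.** The note sets its test at 30% *of* IBW, and the example sets it at 30% *over* IBW. Under the first, IBW is used for practically everyone. Under the second, actual weight is used for everyone up to 1.3 times IBW. Clearance is proportional to the weight entered, so the choice feeds straight into the result.

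**Female constant.** Two formulas offered as alternatives should give the same answer for the same subject. The male constants agree across units; the female ones do not. The disease under study makes the female constant the relevant one at any site that uses the µmol/L line.

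What is at stake is consistent application of one entry criterion across 6 to 10 sites. Two sites could each follow the appendix in good faith and reach opposite decisions on the same woman. SAP Section 6.2 also plans a listing of inclusion and exclusion deviations, and whether a borderline subject belongs in it would depend on the reading chosen.

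**Working it through.** **Inputs.** The threshold is from Section 4.1. The formulas, constants, IBW equations and example are from Section 16.4. The women below are assumed for illustration. The conversion 88.4 µmol/L per mg/dL is also an assumption, since the documents do not give it; it serves only as a second check and to convert one creatinine value.

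**1. The plan's own example**

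- IBW = 50 + 2.3 × (68 − 60) = 68.4 kg, as printed.
- 90 / 68.4 = 1.316, so the subject is 31.6% over IBW, as the example says.
- Cut-off as note 2 is written: 0.30 × 68.4 = 20.5 kg.
- Cut-off as the example applies it: 1.30 × 68.4 = 88.9 kg.

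A 90 kg subject exceeds both cut-offs, so the example's result (use IBW) is the same either way. The conflict is in the test, and the example chosen cannot reveal it.

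**2. Effect of the weight reading**

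The mg/dL formula for women is 0.85 × (140 − age) × weight / (72 × creatinine). At age 70 the numerator constant is 0.85 × 70 = 59.5. Female IBW = 45.5 + 0.906 × (height in cm − 152.4).

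| | Woman A | Woman B |
|---|---|---|
| Age, height, weight | 70 y, 165 cm, 45 kg | 70 y, 160 cm, 65 kg |
| Creatinine | 1.45 mg/dL | 1.6 mg/dL |
| IBW | 45.5 + 0.906 × 12.6 = 56.9 kg | 45.5 + 0.906 × 7.6 = 52.4 kg |
| Weight / IBW | 0.79 | 1.24 |
| Note 2 as written (IBW) | 59.5 × 56.9 / 104.4 = 32.4, eligible | 59.5 × 52.4 / 115.2 = 27.1, not eligible |
| Example's test (actual weight) | 59.5 × 45 / 104.4 = 25.6, not eligible | 59.5 × 65 / 115.2 = 33.6, eligible |

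For woman B, setting CrCl to 30 gives creatinine cut-offs of 59.5 × 52.4 / (72 × 30) = 1.44 mg/dL under the literal rule and 59.5 × 65 / (72 × 30) = 1.79 mg/dL under the example's test. Every value between these is classified differently.

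In general:

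- Below IBW, the literal rule gives the higher clearance.
- From 100% to 130% of IBW, it gives the lower one, and actual weight yields up to 30% more.
- Above 130% of IBW, the two readings coincide.

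**3. Female constant**

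- Ratio of female to male constants: 0.85 / 1.0 = 0.85 in the mg/dL formula, and 1.0 / 1.23 = 0.813 in the µmol/L formula. They should be equal.
- The male pair implies a unit factor of 1.23 × 72 = 88.56. The female K that matches Q = 0.85 is then 0.85 × 1.23 = 1.0455.
- With the assumed factor of 88.4, male K = 88.4 / 72 = 1.228 and female K = 0.85 × 88.4 / 72 = 1.044.
- Shortfall with K = 1.0: 1 / 1.044 = 0.958 and 1 / 1.0455 = 0.956, so 4.2% to 4.4% low.
- Affected band on the mg/dL scale: from 30.0 up to 30 × 1.044 = 31.3 mL/min (31.4 with 1.0455).
- Example: age 70, 60 kg as the weight entered, creatinine 1.6 mg/dL = 141.4 µmol/L. The mg/dL formula gives 59.5 × 60 / 115.2 = 31.0; the µmol/L formula gives 70 × 60 / 141.4 = 29.7.

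**The case against.** The strongest reply is that the appendix corrects itself. The example spells out the test as more than 30% over IBW, and the fallback to actual weight has no purpose under the literal wording. A careful site reader would probably conclude that *of* was written for *over*. On the constant, the µmol/L line is only an alternative, the Synopsis plans sites in the United States alone, and 1.0 might be a rounded 1.04. The affected band is about 1.3 mL/min wide in a trial of 33 to 54 subjects, and nothing in the documents says how many will be near 30.

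Most of this limits the size of the point and stands. It does not remove the conflict. The example gives the same result under both tests, so it cannot show a site that the note is wrong, and both formula lines name ideal body weight, which favours the literal reading. Rounding is a weak explanation when the male constant carries two decimals.

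Three stronger inferences are tempting and should not be drawn:

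- **A safety failure.** A reader might infer that the literal rule credits an underweight woman with renal function she lacks. Both figures are estimates that differ only in the weight entered, and for women between 100% and 130% of IBW the literal rule errs towards exclusion. The documents do not tie renal function to the risk of SL-172154; Protocol Section 3.2 explains rapid clearance by an antigen sink, target-mediated uptake and anti-drug antibodies.
- **A wrong constant applied to every subject.** All subjects are expected to be women, but the constant acts only where the µmol/L line is used, and no section says that any site uses it.
- **A wrong worked example.** Its arithmetic and its conclusion both reproduce.

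**Conclusion.** The point holds as a minor one. Section 16.4 contains two internal contradictions in the text that governs an entry criterion without waivers.

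The weight rule is the larger. In the two illustrative women the readings differ by factors of 56.9 / 45 = 1.26 and 65 / 52.4 = 1.24, in opposite directions, and each woman crosses the threshold. The example and the fallback clause indicate which test was meant, but that is for the sponsor to confirm.

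The constant is worth about 4%, and it has no effect if every site reports mg/dL, which is plausible for United States sites but not stated. Its mismatch can be shown from the appendix's own ratios without any outside conversion factor.

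The illustrative women rest on assumed ages, heights, weights and creatinine values. They show that reclassification can happen, not how often. DLT counting, MTD estimation and the endpoint definitions are unaffected.

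**What to change.** The sponsor should:

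1. Reconcile note 2, the weight label in both formula lines and the worked example into one rule. If the sponsor confirms the example's test, note 2 would call for IBW when actual weight is more than 30% over IBW and for actual weight otherwise, and the formula lines would refer to the weight chosen under note 2.
2. Make the female K agree with Q = 0.85 (about 1.04), or delete the µmol/L line if no site uses it.
3. Preferably add a second example with a woman between 100% and 130% of IBW, where the two readings diverge.

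The cost is a short appendix correction. It could be made at the next amendment, which needs IRB/IEC review under Protocol Section 13.2, or by a clarification memo, a route that the SAP (Section 3.1, Table 1, note e) shows the sponsor already using for infusion times. If enrolment is complete, it is enough to state in the study report which weight rule was applied.

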16.5.1 RECIST v1.1 Criteria

Measurable disease: Measurable tumor lesions (nodal, subcutaneous, lung parenchyma, solid organ metastases) are defined as those that can be accurately measured in at least one dimension (longest diameter to be recorded) as ≥ 10 millimeter (mm) with CT scan or clinical examination. Bone lesions are considered measurable only if assessed by CT scan and have an identifiable soft tissue component that meets these requirements (soft tissue component ≥ 10 mm by CT scan). Malignant lymph nodes must be ≥ 15 mm in the short axis to be considered measurable; only the short axis will be measured and followed. All tumor measurements must be recorded in mm (or decimal fractions of cm). Previously irradiated lesions are not considered measurable unless progression has been documented in the lesion.

Malignant lymph nodes: pathological nodes must meet the criterion of a short axis of ≥ 15 mm by CT scan and only the short axis of these nodes will contribute to the baseline sum. All other pathological nodes (those with short axis ≥ 10 mm but < 15 mm) should be considered non-target lesions. Nodes that have a short axis < 10 mm are considered non-pathological and should not be recorded or followed.

Non-measurable disease: All other lesions (or sites of disease), including small lesions (longest diameter <10 mm [<1 cm] or pathological lymph nodes with \ge 10 to <15 mm [\ge 1 to <1.5 cm] short axis), are considered non-measurable disease. Bone lesions without a measurable soft tissue component, leptomeningeal disease, ascites, pleural/pericardial effusions, lymphangitis cutis, inflammatory breast disease, lymphangitic involvement of lung or skin, and abdominal masses followed by clinical exam are all non-measurable. Lesions in previously irradiated areas are non-measurable, unless progression has been demonstrated.

Note: Cystic lesions that meet the criteria for radiographically defined simple cysts should not be considered as malignant lesions (neither measurable nor non-measurable) since they are, by definition, simple cysts.

'Cystic lesions' thought to represent cystic metastases can be considered as measurable lesions, if they meet the definition of measurability described above. However, if non-cystic lesions are present in the same participant, these are preferred for selection as target lesions.

Target lesions: When more than one measurable tumor lesion is present at baseline all lesions up to a maximum of 5 lesions in total (and a maximum of 2 lesions per organ), representative of all involved organs, should be identified as **target lesions** and recorded and measured at baseline. Target lesions should be selected on the basis of their size (lesions with the longest diameter), be representative of all involved organs, but in addition should be those that lend themselves to reproducible repeated measurements. It may be the case that, on occasion, the largest lesion which can be measured reproducible measurement in which circumstance the next largest lesion which can be measured reproducibly should be selected. A sum of the diameters (longest for non-nodal lesions, short axis for nodal lesions) for all target lesions will be calculated and reported as the baseline sum diameters. If lymph nodes are to be included in the sum, then only the short axis is added into the sum. At baseline, the sum of the target lesions (longest diameter of tumor lesions plus short axis of lymph nodes: overall maximum of 5) is to be recorded.

After baseline, a value should be provided on the eCRF for all identified target lesions for each assessment, even if very small. If extremely small and faint lesions cannot be accurately measured but are deemed to be present, a default value of 5 mm may be used. If lesions are too small to measure and indeed are believed to be absent, a default value of 0 mm may be used. The baseline sum diameters will be used as reference to further characterize any objective tumor regression in the measurable dimension of the disease.

Non-target lesions: All non-measurable lesions (or sites of disease) plus any measurable lesions over and above those listed as target lesions are considered **non-target lesions** and should also be recorded at baseline. Measurements of these lesions are not required, but the presence, absence, or in rare cases unequivocal progression of each should be noted throughout follow-up.

16.5.2 Evaluation of Response

Complete Response (CR): Disappearance of target and non-target lesions and normalization of tumor markers. Pathological lymph nodes must have short axis measures <10 mm (Note: continue to record the measurement even if <10 mm and considered CR). Residual lesions (other than nodes <10 mm) thought to be non-malignant should be further investigated (by cytology, specialized imaging or other techniques as appropriate for individual cases) before CR can be accepted. Response should be confirmed in a subsequent scan ≥ 4 weeks after the scan showing CR.

Partial Response (PR): At least a 30% decrease in the sum of the measures (longest diameters for tumor lesions and short axis measure for nodes) of target lesions, taking as reference the baseline sum of diameters. Non-target lesions must be non-progressive disease. Response should be confirmed in a subsequent scan \geq 4 weeks after the scan showing PR.

Stable Disease (SD): Neither sufficient shrinkage to qualify for PR nor sufficient increase to qualify for progressive disease, taking as reference the smallest sum diameters while on study. Documented at least once \geq 4 weeks from baseline.

Progressive Disease (PD): At least a 20% increase in the sum of diameters of measured lesions taking as references the smallest sum of diameters recorded on study (including baseline) AND an absolute increase of \geq 5 mm. Appearance of new lesions will also constitute progressive disease (including lesions in previously unassessed areas). In exceptional circumstances, unequivocal progression of non-target disease may be accepted as evidence of disease progression, where the overall tumor burden has increased sufficiently to merit discontinuation of treatment or where the tumor burden appears to have increased by at least 73% in volume. Modest increases in the size of one or more non-target lesions are NOT considered unequivocal progression. If the evidence of progressive disease is equivocal (target or non-target), treatment may continue until the next assessment, but if confirmed, the earlier date must be used.

16.5.3 iRECIST v1.1 Criteria

When using iRECIST, the definitions of measurable and non-measurable lesions still follow RECIST v1.1. The principles used to establish an objective tumor response when using iRECIST are largely unchanged from RECIST v1.1, however, responses assigned using iRECIST have a prefix of "i" (e.g., "immune" complete response [iCR]) to differentiate them from responses assigned using RECIST v1.1.

CONFIDENTIAL Compound: SL-172154

The major change is the concept of resetting the bar if RECIST v1.1 progression is followed at the next assessment by tumor shrinkage. This adaptation accounts for instances where an increase in tumor burden, or the appearance of new lesions, does not reflect true tumor progression. Therefore, iRECIST requires confirmation of progression.

Confirming Progression: iRECIST requires the confirmation of progression and uses the terms iUPD (unconfirmed progression) and iCPD (confirmed progression). Confirmatory scans should be performed at least 4 weeks, but no longer than 8 weeks after iUPD. iCPD is confirmed if further increase in tumor burden, compared to the last assessment, is seen as evidenced by one or more of the following criteria:

- Continued increase in tumor burden (from iUPD) where RECIST v1.1 definitions of progression had been met (from nadir) in target, non-target disease or new lesions.
 - Progression in target disease worsens with an increase of at least 5 mm in the absolute value of the sum
 - Continued unequivocal progression in non-target disease with an increase in tumor burden
 - Increase in size of previously identified new lesion (s) (an increase of at least 5 mm in the absolute value of the sum of those considered to be target new lesions) or additional new lesions
- RECIST v1.1 criteria are met in lesions types (target or non-target or new lesions) where progression was not previously identified, including the appearance of additional new lesions.
- If iUPD is not confirmed at the next assessment, then the appropriate response will be assigned (iUPD if the criteria are still met, but no worsening, or iSD, iPR or iCR if those criteria are met compared to baseline).

New Lesions: New lesions (NL) should be assessed and measured as they appear using RECIST v1.1 criteria (maximum of 5 lesions, no more than 2 per site, at least 10 mm in long axis (or 15 mm in short axis for nodal lesions) and recorded as New Lesions-Target (NLT) and New Lesion-Non-Target (NLNT) to allow clear differentiation from baseline target and non-target lesions.

New lesions may either meet the criteria of NLT or NLNT to drive iUPD (or iCPD). However, the measurements of target lesions should NOT be included in the sum of measures of original target lesions identified at baseline. Rather, these measurements will be collected on a separate table in the eCRF.

Progressive disease is confirmed in the New Lesion category if the next imaging assessment, conducted at least 4 weeks (but not more than 8 weeks) after iUPD confirms further progression from iUPD with either an increase of at least 5 mm in the absolute value of the sum of NLT OR an increase (but not necessarily unequivocal increase) in the size of NLNT lesions OR the appearance of additional new lesions.

	Non-Target Lesions	New Lesions	Time Point Response	
Target Lesions			No prior iUPD	Prior iUPD
iCR	iCR	No	iCR	iCR
iCR	Non-iCR/Non- iUPD	No	iPR	iPR

iRECIST Time Point Response Table

	Non-Target Lesions	New Lesions	Time Point Response	
Target Lesions			No prior iUPD	Prior iUPD
iPR	Non-iCR/Non- iUPD	No	iPR	iPR
iSD	Non-iCR/Non- iUPD	No	iSD	iSD
iUPD with no change OR decrease from last TP	iUPD with no change OR decrease from last TP	Yes	NA	NLs confirms iCPD if NL were previously identified and increase in size (≥5 mm in SOM for NLT or any increase for NLNT) or number. If no change in NLs (size or number) from last TP, remains iUPD
iSD	iUPD	No	iUPD	Remains iUPD unless iCPD confirmed based in further increase in size of NT disease (need not meet RECIST v1.1 criteria for unequivocal PD)
iUPD	iUPD	No	iUPD	Remains iUPD unless iCPD confirmed based on further increase in SOM of at least 5 mm, otherwise remains iUPD
iUPD	iUPD	No	iUPD	Remains iUPD unless iCPD confirmed based on further increase in previously identified T lesion iUPD SOM ≥5 mm and/or NT lesion iUPD (prior assessment need not be unequivocal PD)
iUPD	iUPD	Yes	iUPD	 Remains iUPD unless iCPD confirmed based on further increase in: previously identified T lesion iUPD SOM ≥5 mm and/ previously identified NT lesion iUPD (prior assessment need not be unequivocal PD) size or number of new lesions previously identified
Non-iUPD/PD	Non-iUPD/PD	Yes	iUPD	 Remains iUPD unless iCPD confirmed based on: increase in size or number of new lesions previously identified

	Non-Target Lesions	New Lesions	Time Point Response		
Target Lesions			No prior iUPD	Prior iUPD	
iUPD iUPD * Using RECIST v1.1 principles. If no pseudo-progression of disease (PSPD) occurs, RECIST v1.1 and iRECIST categories for CR, PR and SD would be the same. ** in any lesion category. *** previously identified in assessment immediately prior to this TP. PD = progressive disease; SOM = sum of measurements Note: Participants with a global deterioration of health status requiring discontinuation of treatment without objective evidence of disease progression at that time should be reported as "symptomatic deterioration." Every effort should be made to document the objective progression even after discontinuation of treatment.					

16.6 Summary of Changes for Protocol Amendment 02

Minor Editorial Changes:

- Title Page and all page headers have edits to denote version number/date of Amendment 02
- Updated TOC and List of Abbreviations
- Removed United Kingdom as a country for location of clinical sites from Synopsis section (Planned Number of Sites and Countries section)
- In Section 3.5.1 clarified that medications are prohibited during SL-172154 therapy (removed study)
- Text deleted from footnote m to SOA table in 6.1: CA-125 should be measured to coincide with each scheduled tumor assessment as outlined above with the last required sample obtained at the post treatment visit which occurs within 30 days of last dose of SL 172154Table 4
- Section 6.1.1 Table 4 title heading added new text: *and RBC Binding*
- In Section 7.3 removed first sentence in last paragraph of this section: Changes in the severity of an AE will be documented to allow an assessment of the duration of the event at each level of severity.

Changes Made to Address FDA Concerns:

1. Homologous recombinant deficiency (HRD) status will be collected for all subjects including BRCA status

Section 6.1 SOA Table and footnotes

- Revised to include collection of HRD information during screening and footnote S provided new text provided in italics as follows: *Homologous recombinant deficiency (HRD) status*: *Collection of HRD status (including BRCA status) is required for all subjects during the screening period. Results from standard of care testing will be used.*
- Footnotes T and U are now associated with Post Treatment and Follow up visits, respectively
- 2. Inclusion criteria revised to allow enrollment of subjects who fulfill the definitions below:
 - a) all subjects with primary ovarian, peritoneal and fallopian cancers are required to have received platinum-based therapies.
 - b) HRD positive subjects if they have failed prior PARP inhibitor therapy given with or without bevacizumab and,
 - c) refractory or intolerant to existing therapy(ies) known to provide clinical benefit for their condition.

Section 4.1 inclusion criterion #3 revised as follows:

3. New Text provided in italics: Subjects should not be eligible for further platinum therapy. Subjects must be refractory or intolerant to existing therapy(ies) known to provide clinical benefit for their condition. Subject must have received platinum-based therapies, and should not be eligible for further platinum therapy, or should be intolerant to such therapy. Subjects with HRD positive disease may participate if they have received prior polyadenosine diphosphate ribose polymerase (PARP) inhibitor therapy given alone or with bevacizumab. 3. Treatment beyond progression per iRECIST requires that subjects have no decline in their ECOG performance status.

Section 8.2 provided new text in the 1st paragraph of this section as indicated (new text in italics):

- Subjects will be permitted to continue IP beyond initial progressive disease provided the subject does not have clinical symptoms of progression, is tolerating IP, *has experienced no decline in ECOG performance status* and is gaining clinical benefit as assessed by the investigator. The subject must be made aware of the potential benefits and risks of continuing the IP in the setting of progressive disease by signing a separate written informed consent.
- 4. The DLT assessment period for assessment of AEs that inform dose escalation decisions is 28 days (not 21 days as originally proposed).

Study Schema revised to note 28-day DLT assessment period

Synopsis Sections that include revisions indicating 28-day DLT assessment period:

• Study Design, Definition of DLT, and Statistical Analysis Sections

Protocol sections revised that include text revisions indicating 28-day DLT assessment period (replacing 21-day period)

- Section 3.1 Description of Study Design
- Section 3.3 Description of Dose Escalation Plan
- Section 3.4 Definition of Dose Limiting Toxicity
- Section 9.2.1 Analysis Populations (revised DLT evaluable population definition)
- 5. Provided further clarification of the intent to monitor subjects for 90 days after SL-172154 treatment is permanently discontinued.

Protocol sections with text revisions providing clarification of 90-day follow up post last dose of study therapy

- Section 6.1 SOA table footnote p revised as follows (new text in italics):
 - p. AE Monitoring: Subjects will be followed continuously for AEs during the study and for 90 days after the last dose of SL-172154. After a subject is discontinued from SL-172154 or study therapy due to progressive disease or for other reasons, any ongoing AE should be followed until resolution (or return to baseline) and documented in the eCRF. If another anti-cancer agent is started within 90 days after the last dose of SL-172154, only SAEs and AEs that occur prior to the start of the new anticancer therapy within 30 days from last dose of SL 172154 should be recorded. In the event of a continuing SAE or a non-serious irAE, the subject will be asked to return for follow-up until the SAE or AE has resolved or is deemed to be continuing indefinitely. AEs will be characterized per NCI-CTCAE criteria v5.0 and events recorded in the eCRF.

• Section 7 text revision (new text in italics)

Subjects will be followed continuously for *allny* AEs starting when a subject has signed the ICF, throughout the course of treatment and for 90 days after the last dose of IP. After a subject is discontinued from SL-172154 due to progressive disease or for other reasons, any ongoing AEs should be followed until resolution (or return to baseline) and documented in the eCRF. If another anti-cancer agent is started *within 90 days after the last dose of SL-172154*, only SAEs and irAEs that occur *prior to starting the new anticancer therapy* within 30 days from last dose of SL 172154 should be recorded. All observed or volunteered AEs (serious or non-serious) and abnormal laboratory test findings, if applicable, whether suspected to have a causal relationship to SL-172154 or not will be recorded in the subject medical record and in the eCRF. AEs will be graded according to NCI-CTCAE v5.0. For all AEs, sufficient information will be pursued and/or obtained to permit an adequate determination of seriousness and outcome of the event (i.e., whether it should be classified as a SAE or not) and an assessment of the causal relationship between the AE and SL-172154. AEs will be followed until resolution (or return to baseline) or stabilization. Refer to Section 7.4 for documentation and reporting of AEs.

• Section 7.4 AE Reporting procedures (new text in italics)

Subjects will be followed continuously for AEs during the study and for 90 days after the last dose of IP. After a subject is discontinued from IP due to progressive disease or for other reasons, any ongoing AE should be followed until resolution (or return to baseline) and documented in the eCRF, regardless of whether the event(s) is attributed to trial medication. If another anti-cancer agent is started *within 90 days of the last dose of SL-172154*, only SAEs and irAEs that occur *before the new anticancer therapy* -within 30 days from last dose of SL-172154 should be recorded. The following information will be recorded: description, date of onset and end date, severity, assessment of relatedness to trial medication, and action taken. Follow-up information should be provided as necessary. AEs will be followed either until resolution, or the event is considered stable.

6. Revised the DLT criteria to include any deaths that are not clearly due to the underlying disease or extraneous causes.

Section 3.4 Definition of Dose Limiting Toxicity and Corresponding Section in Synopsis

- New Text: Any death not clearly related to underlying disease or extraneous causes
- 7. Clarified that subjects eligible for dose escalation must have tolerated SL-172154 therapy well and experienced AEs < or = Grade 1 in severity on the most recent cycle of study treatment.

Section 3.3.1 Intrasubject Dose Escalation (and in Synopsis) revised to include new text in italics

• Intrasubject dose escalation(s) may be considered on a case-by-case basis, provided that the subject has completed at least 2 cycles at the originally assigned dose, has tolerated treatment well, and did not experience Grade 3 or higher toxicity, and experienced ≤ Grade 1 toxicity on the most recent cycle of SL-172154 therapy.

8. Clarified that all AEs that occur in subjects enrolled in this study will be collected starting from the time subject consents to participate until they are discontinued from the study.

Section 7.1.1 Events not Qualifying as AEs/SAEs

• New text added: Because attribution of AEs is difficult in a FIH study, any toxicity experienced by subjects in this study should be recorded as AEs unless otherwise specified.

16.7 Summary of Changes for Protocol Amendment 03

Minor Editorial Changes:

- Title Page and all page headers have edits to denote version number/date of Amendment 03
- Reference to Investigator's Brochure (IB) for SL-172154 updated and IB now cited in section 1.4.1 point #3 Hemolysis and Anemia
- Updated TOC
- Updated document numbers denoted for Amendments 1 and 2 as shown below

Shattuck Labs Document Number	Date	Version
SL03-OHD-01_01 00	03 March 2020	Amendment No. 1
SL03-OHD-01_02 01	24 April 2020	Amendment No. 2

- Section 1.2.4 last sentence of 2nd paragraph text removed: Additionally, SL-172154 was evaluated in vitro for potential binding to erythrocytes and hemolysis
- Section 1.2.4 second sentence of 7th paragraph new text added (shown in italics) and text removed: In vitro incubation of SL-172154 with erythrocytes from cynomolgus monkeys or humans *whole blood* did not result in any detectable hemolysis.
- Section 1.2.4 the last sentence of the last paragraph had text removed: Overall, the nonclinical safety assessment program supports the administration of SL-172154 as an intravenous infusion in the proposed first-in-human (FIH) clinical study SL03-OHD-101.
